#### **5.2.4.b Exceptions to Permanent Discontinuation**

- Potentially reversible inflammation (< Grade 4), attributable to a local anti-tumor reaction and a potential therapeutic response. This includes inflammatory reactions at

sites of tumor resections or in draining lymph nodes, or at sites suspicious for, but not diagnostic of metastasis.

- Hospitalization for  $\leq$  Grade 2 adverse events where the primary reason for hospitalization is to expedite the clinical work-up.
- Patients with the following conditions where in the investigator's opinion continuing study drug administration is justified:
  - Ocular toxicity that has responded to topical therapy (eg, ocular steroids).
  - Endocrinopathies where clinical symptoms are controlled with appropriate hormone replacement therapy. **Note:** Ipilimumab may not be restarted while the patient is being treated with systemic corticosteroids except for patients on stable doses of hormone replacement therapy such as hydrocortisone.

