## **Nivolumab Combined with Ipilimumab**

In the Phase 1 study CA209004, ascending doses of nivolumab have been studied concomitantly with ascending doses of ipilimumab in subjects with unresectable or metastatic melanoma. In each arm in this multi-arm study, ipilimumab was administered once every 3 weeks for 4 doses with nivolumab administered once every 3 weeks for 8 doses. Starting at week 24, ipilimumab and nivolumab were administered once every 12 weeks for 8 doses. The three initial dose-escalation cohorts consisted of Cohort 1 (nivolumab 0.3 mg/kg plus ipilimumab 3 mg/kg; n=14), Cohort 2 (nivolumab 1.0 mg/kg plus ipilimumab 3 mg/kg; n=17) and Cohort 3 (nivolumab 3.0 mg/kg plus ipilimumab 3 mg/kg; n=6). Later, the study was amended to include Cohort 2a which evaluated nivolumab 3 mg/kg plus ipilimumab 1 mg/kg (n=16). The following DLTs were observed in Cohort 1 - Grade 3 elevated AST/ALT (1 subject); in Cohort 2 - Grade 3 uveitis (1 subject) and Grade 3 elevated AST/ALT (1 subject) and in Cohort 3 - Grade 4 elevated lipase (2 subjects) and Grade 3 elevated lipase (1 subject). Based on these data, Cohort 2 was identified as the maximum tolerated dose (MTD) and Cohort 3 exceeded the MTD.

As of 15-Feb-2013, a total of 53 melanoma subjects were treated with nivolumab combined with ipilimumab in CA209004 across cohorts 1, 2, 2a, and 3. At least one AE regardless of causality has been reported in 98% of subjects treated. The most common (reported at > 10% incidence) treatment related AEs (any Grade %; Grade 3-4 %: 93; 53) are rash (55; 4), pruritus (47; 0), vitiligo (11; 0), fatigue (38; 0), pyrexia (21, 0), diarrhea (34; 6), nausea (21, 0), vomiting (11, 2), ALT increased (21; 11), AST increased (21; 13), lipase increased (19; 13), amylase increased (15, 6), headache (11, 0), and cough (13, 0).

The majority of AEs leading to discontinuation (regardless of causality) were Grade 3 or 4 (reported in 11 of 53 subjects, 21%). Grade 3 events included lipase increased, ALT increased, AST increased, troponin I increased, colitis, diverticular perforation, pancreatitis, tachycardia, renal failure acute, choroiditis, autoimmune disorder, and pneumonitis. One subject each discontinued due to Grade 4 events of blood creatinine increased and AST increased. No drug-related deaths were reported.

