### **5.2.3 Discontinuation of Study Therapy**

Subjects **MUST** be discontinued from study therapy **AND** withdrawn from the study for the following reasons:

- Any Grade 2 drug-related uveitis or eye pain or blurred vision that does not respond to topical therapy and does not improve to Grade 1 severity within the re-treatment period **OR** requires systemic treatment
- Any Grade 3 non-skin, drug-related adverse event lasting > 7 days, with the following exceptions for drug-related laboratory abnormalities, uveitis, pneumonitis, bronchospasm, diarrhea, colitis, neurologic toxicity, hypersensitivity reactions, and infusion reactions:
  - Grade 3 drug-related uveitis, pneumonitis, bronchospasm, diarrhea, colitis, neurologic toxicity, hypersensitivity reaction, or infusion reaction of any duration requires discontinuation
  - Grade 3 drug-related laboratory abnormalities do not require treatment discontinuation except:
    - Grade 3 drug-related thrombocytopenia > 7 days or associated with bleeding requires discontinuation
    - Any drug-related liver function test (LFT) abnormality that meets the following criteria require discontinuation:
      - AST or ALT > 8 x ULN
      - Total bilirubin > 5 x ULN
      - Concurrent AST or ALT > 3 x ULN and total bilirubin > 2 x ULN
- Any Grade 4 drug-related adverse event or laboratory abnormality, except for the following events which do not require discontinuation:
  - Grade 4 amylase or lipase abnormalities that are not associated with symptoms or clinical manifestations of pancreatitis. It is recommended to consult with the BMS Medical Monitor for Grade 4 amylase or lipase abnormalities.

□ Isolated Grade 4 electrolyte imbalances/abnormalities that are not associated with clinical sequelae and are corrected with supplementation/appropriate management within 72 hours of their onset

□ Any dosing interruption lasting > 6 weeks with the following exceptions:

□ Dosing interruptions to allow for prolonged steroid tapers to manage drug-related adverse events are allowed. Prior to re-initiating treatment in a subject with a dosing interruption lasting > 6 weeks, the PI will discuss feasibility with the sponsor.. Tumor assessments should continue as per protocol even if dosing is interrupted.

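### For controlled Grade 3 uveitis and controlled Grade 3 (over 7 days) or Grade 4 endocrinopathy, the mandatory stop in 5.2.3 meets a discretionary permission to continue in 5.2.4.b, and no precedence is stated

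*Combined protocol and SAP*

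**What the plan says.** Section 5.2.3 is a mandatory list: patients on it must stop study therapy and be "withdrawn from the study for the following reasons". Three entries matter here, all limited to drug-related events.

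- "Grade 3 drug-related uveitis, pneumonitis, bronchospasm, diarrhea, colitis, neurologic toxicity, hypersensitivity reaction, or infusion reaction of any duration requires discontinuation".
- "Any Grade 3 non-skin, drug-related adverse event lasting > 7 days". The exceptions cover laboratory abnormalities and a list of named events that have their own rule. Endocrinopathy is not among them.
- Grade 4 events. The only exceptions are certain amylase or lipase abnormalities and certain isolated electrolyte abnormalities.

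Section 5.2.4.b lists exceptions to permanent discontinuation. If the investigator judges that continuing study drug is justified, it may continue for "Ocular toxicity that has responded to topical therapy (eg, ocular steroids" and for "Endocrinopathies where clinical symptoms are controlled with appropriate hormone replacement therapy". Neither item has a ceiling on grade or duration. A separate item exempts "Potentially reversible inflammation (< Grade 4), attributable to a local anti-tumor reaction", again without a limit on duration.

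The resume criteria in 5.2.2 add that endocrinopathies adequately controlled on physiologic replacement may resume treatment, with no grade cap.

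**The concern.** Two sites, or one site on two days, could treat the same patient differently and each point to protocol text in support. Under 5.2.3 the patient stops both drugs and leaves the study. Under 5.2.4.b the investigator may go on dosing after a Grade 3 or Grade 4 immune event.

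Safety is the first thing at stake. Exposure, the count of discontinuations for toxicity and time on study also depend on which section is followed. Follow-up changes too: under section 3.4, patients removed for unacceptable toxicity have later efficacy assessments by standard of care and not on the protocol schedule. Eye events deserve a clear rule in a uveal melanoma population.

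**Working it through.** This is a comparison of rules. The plan gives no figure for this point, so there is none to reproduce. All events below are drug-related.

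| Event | 5.2.3 | 5.2.4.b | Resume criteria (5.2.2) | Result |
|---|---|---|---|---|
| Grade 2 uveitis that responds to topical therapy | Not triggered unless systemic treatment is needed | May continue | General rule | No conflict on topical response |
| Grade 3 uveitis that responds to topical therapy | Stop and withdraw, any duration | May continue | No eye-specific line | Conflict |
| Grade 3 endocrinopathy, below Grade 3 within 7 days | Not triggered | May continue | May resume once controlled | No conflict |
| Grade 3 endocrinopathy over 7 days, controlled on replacement | Stop and withdraw | May continue | May resume | Conflict |
| Grade 4 endocrinopathy, controlled on replacement | Stop and withdraw | May continue | May resume | Conflict |
| Grade 3 tumour-site inflammation over 7 days | Stop and withdraw, if classed as a drug-related adverse event | Exempt | No specific line | Possible conflict |

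In 5.2.3, response to topical treatment matters at Grade 2 but not at Grade 3. Sections 5.2.4.a and 5.2.4.b make that response decisive without naming a grade. That difference produces the uveitis row.

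**Looking for a tie-breaker.** No sentence says that 5.2.3 overrides 5.2.4.b, or that 5.2.4.b limits only 5.2.4.a. For discontinuation parameters the resume criteria point to a section 4.3.5 that does not exist (4.3 is the monitoring plan). Sections 5.2.4.a, 5.2.5 and 5.2.6.b send the reader to Appendix B, but the algorithms are in Appendix A. That appendix describes itself as guidance and has no ocular algorithm. Its endocrine figure is not in the text available, so nothing is inferred from it.

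**What the documents allow on frequency.**

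- Uveitis: section 1.3.6 reports, among the dose-limiting toxicities of the phase 1 combination study, "in Cohort 2 - Grade 3 uveitis (1 subject") among 17 patients at this trial's induction doses. 1/17 = 5.9%. The exact lower 95% limit solves 1 − (1 − p)^17 = 0.025, so p = 0.1%. The upper limit solves (1 − p)^17 + 17p(1 − p)^16 = 0.025, so p = 28.7%.
- Endocrine: section 1.3.6 gives 3% Grade 3/4 endocrine disorders on ipilimumab alone at 3 mg/kg. It gives no combination rate.
- Scaled: 27 × 1/17 = 1.6 and 39 × 1/17 = 2.3 for uveitis; 27 × 3% = 0.8 and 39 × 3% = 1.2 for endocrine events.

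These count every such event. The conflict needs the subset that responded to topical treatment, or that was controlled on replacement after more than 7 days at Grade 3 or after reaching Grade 4. The documents give neither fraction.

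**Decision rule.** Rejecting at 4 or more responders of 27 gives an exact type I error of 0.0437 at a 5% response rate and a type II error of 0.1823 at 20%. Section 9 states 4.4% and 18.2%. Both reproduce, and neither depends on the discontinuation rules.

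**The case against.** The best defence is structural. Section 5.2.4 is headed for ipilimumab, and the ocular exception in 5.2.4.b mirrors a trigger in 5.2.4.a: unresponsive to topical treatment there, responsive here. So 5.2.4.b reads naturally as an exception to 5.2.4.a alone, leaving the mandatory list in 5.2.3 untouched. A site that stops treatment complies with both sections, because one says must and the other says may. Ipilimumab is given only at weeks 1, 4, 7 and 10, so on this reading 5.2.4.b has nothing to govern in maintenance. The resume criteria can likewise be read as applying only to patients who have not already met a discontinuation criterion.

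Much of this stands as a plausible reading, and it shows that the clash is a mandatory stop against a discretionary permission, not two opposite commands. It does not settle the matter. The limit is nowhere stated, and 5.2.4.b speaks of study drug, not ipilimumab. Stopping study therapy under 5.2.3 includes ipilimumab, so for ipilimumab in induction the two sections still differ. The heading also cannot explain the endocrinopathy line in 5.2.2, which applies to study drug generally.

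The objection is also right that tumour-site inflammation is weaker ground. Section 5.2.4.b describes it as a local anti-tumour reaction and a potential therapeutic response, and 5.2.3 applies only if it is also classed as a drug-related adverse event.

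**Conclusion.** The inconsistency is real and should be corrected. It is limited to drug-related events in the overlap: Grade 3 uveitis that responds to topical therapy, and endocrinopathy controlled on replacement that was Grade 3 for more than 7 days or Grade 4. Tumour-site inflammation below Grade 4 is a possible further case, only if it counts as a drug-related adverse event lasting more than 7 days. If the ipilimumab heading governs, the 5.2.4.b conflict is confined to induction; the text does not say whether it does.

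Two stronger inferences are tempting. By adding the scaled counts (1.6 + 0.8 = 2.4, and 2.3 + 1.2 = 3.5), a reader might conclude that about 2 to 4 patients could be handled either way. The documents do not support this. The sums count all such events and not the overlap, the uveitis figure rests on one event with a very wide interval, the endocrine figure is for one drug, and 39 includes a 5% allowance for screen failures. The rates are rough upper indications only.

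A reader might also infer a threat to the primary result, since 4 responders decide it. None is shown. Section 3.2.1.c asks for the week 12 assessment even after stopping for a drug-related event, section 6.4.3.e counts all available assessments before subsequent therapy, and section 3.4 keeps recording deaths.

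The conclusion rests on the plain text and depends on no frequency. It takes no view on which clinical rule is right.

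**What to change.** Reconcile 5.2.3, the resume criteria in 5.2.2, 5.2.4.a and 5.2.4.b in one discontinuation table for ocular and endocrine events, and for tumour-site inflammation if the sponsor counts it as drug-related. For each event, the table should give the grade, the duration, the drug or drugs concerned, the study phase, and whether an exception applies. Each section should state which one prevails, and 5.2.4.b should state whether it limits only 5.2.4.a. The section and appendix cross-references should be corrected at the same time. The sponsor and medical monitor decide the clinical content of the table.

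The cost is a clarifying amendment and site retraining, with no added visits, tests or patients.

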### **5.2.5 Immune-Related Adverse Events (irAEs) Reactions and Immune-mediated Adverse Reactions: Definition, Monitoring, and Treatment**

Blocking CTLA-4 and PD-1 function may permit the emergence of auto-reactive T cells and resultant clinical autoimmunity. Rash/vitiligo, diarrhea/colitis, uveitis/episcleritis, hepatitis, and hypopituitarism were drug-related, presumptive autoimmune events, now termed immune-mediated adverse reactions, noted in previous ipilimumab studies.

For the purposes of this study, an immune-related adverse reaction is defined as an adverse reaction of unknown etiology associated with drug exposure and consistent with an immune phenomenon. Efforts should be made to rule out neoplastic, infectious, metabolic, toxin or other etiologic causes prior to labeling an event an immune-related adverse reactions. Serologic, immunologic, and histologic (biopsy) data should be used to support the diagnosis of an immune-related toxicity. Suspected immune-related adverse reactions must be documented on an AE or SAE form. Another term for an irAE is an immune-mediated adverse reaction, as it is termed in the Ipilimumab US Prescribing Information. Both terms may be used in this protocol document.

Patients should be informed of and carefully monitored for evidence of clinically significant systemic immune-mediated adverse reactions (e.g., systemic lupus erythematosus-like diseases) or organ-specific immune-mediated adverse reaction (e.g., rash, colitis, uveitis, hepatitis or thyroid disease). If an immune-mediated adverse reaction is noted, appropriate work-up (including biopsy if possible) should be performed, and steroid therapy may be considered if clinically necessary.

It is unknown if systemic corticosteroid therapy has an attenuating effect on ipilimumab activity. However, clinical anti-tumor responses have been maintained in patients treated with corticosteroids and discontinued from ipilimumab. If utilized, corticosteroid therapy

should be individualized for each patient. Prior experience suggests that colitis manifested as  $\geq$  Grade 3 diarrhea requires corticosteroid treatment.

Specific treatment algorithms for immune-mediated adverse reactions adverse events are included as appendices B.

### **5.2.6 Other Guidance**

**Treatment of Nivolumab or Ipilimumab Related Infusion Reactions** Since nivolumab and ipilimumab contains only human immunoglobulin protein sequences, it is unlikely to be immunogenic and induce infusion or hypersensitivity reactions. However, if such a reaction were to occur, it might manifest with fever, chills, rigors, headache, rash, pruritis, arthralgias, hypo- or hypertension, bronchospasm, or other symptoms. All Grade 3 or 4 infusion reactions should be reported within 24 hours to the BMS Medical Monitor and reported as an SAE if criteria are met. Infusion reactions should be graded according to NCI CTCAE (version 4.0) guidelines.

Treatment recommendations are provided below and may be modified based on local treatment standards and guidelines as appropriate:

For mild symptoms, Grade 1 (Mild reaction; infusion interruption not indicated; intervention not indicated) Remain at bedside and monitor subject until recovery from symptoms. The following prophylactic premedications are recommended for future infusions: diphenhydramine 50 mg (or equivalent) and/or paracetamol 325 to 1000 mg (acetaminophen) at least 30 minutes before additional nivolumab administrations. For moderate symptoms, Grade 2

- (Moderate reaction requires therapy or infusion interruption but responds promptly to symptomatic treatment [eg, antihistamines, non-steroidal anti-inflammatory drugs, narcotics, corticosteroids, bronchodilators, IV fluids]; prophylactic medications indicated for  $\leq$  24 hours). Stop the nivolumab or ipilimumab infusion, begin an IV infusion of normal saline, and treat the subject with diphenhydramine 50 mg IV (or equivalent) and/or paracetamol 325 to 1000 mg (acetaminophen); remain at bedside and monitor subject until resolution of symptoms. Corticosteroid or bronchodilator therapy may also be administered as appropriate. If the infusion is interrupted, then restart the infusion at 50% of the original infusion rate when symptoms resolve; if no further complications ensue after 30 minutes, the rate may be increased to 100% of the original infusion rate. Monitor subject closely. If symptoms recur then no further nivolumab or ipilimumab will be administered at that visit. Administer diphenhydramine 50 mg IV, and remain at bedside and monitor the subject until resolution of symptoms. The amount of study drug infused must be recorded on the electronic case report form (eCRF). The following prophylactic premedications are recommended for future infusions: diphenhydramine 50 mg (or equivalent) and/or paracetamol 325 to 1000 mg (acetaminophen) should be administered at least 30

minutes before additional nivolumab or ipilimumab administrations. If necessary, corticosteroids (recommended dose: up to 25 mg of IV hydrocortisone or equivalent) may be used.

For severe symptoms, Grade 3 or Grade 4

(Severe reaction, Grade 3: prolonged [ie, not rapidly responsive to symptomatic medication and/or brief interruption of infusion]; recurrence of symptoms following initial improvement; hospitalization indicated for other clinical sequelae [eg, renal impairment, pulmonary infiltrates]). Grade 4: (life-threatening; pressor or ventilator support indicated).

- Immediately discontinue infusion of nivolumab or ipilimumab. Begin an IV infusion of normal saline, and treat the subject as follows. Recommend bronchodilators, epinephrine 0.2 to 1 mg of a 1:1,000 solution for subcutaneous administration or 0.1 to 0.25 mg of a 1:10,000 solution injected slowly for IV administration, and/or diphenhydramine 50 mg IV with methylprednisolone 100 mg IV (or equivalent), as needed. Subject should be monitored until the investigator is comfortable that the symptoms will not recur. Nivolumab or ipilimumab will be permanently discontinued. Investigators should follow their institutional guidelines for the treatment of anaphylaxis. Remain at bedside and monitor subject until recovery from symptoms. In the case of late-occurring hypersensitivity symptoms (eg, appearance of a localized or generalized pruritis within 1 week after treatment), symptomatic treatment may be given (eg, oral antihistamine, or corticosteroids).

#### **5.2.6.a Treatment of Nivolumab or Ipilimumab-Related Isolated Drug Fever**

In the event of isolated drug fever, the investigator must use clinical judgment to determine if the fever is related to the ipilimumab or to an infectious etiology. If a patient experiences isolated drug fever, for the next dose, pre-treatment with acetaminophen or non-steroidal anti-inflammatory agent (investigator discretion) should be instituted and a repeated antipyretic dose at 6 and 12 hours after ipilimumab infusion, should be administered. The infusion rate will remain unchanged for future doses. If a patient experiences recurrent isolated drug fever following premedication and post dosing with an appropriate antipyretic, the infusion rate for subsequent dosing should be decreased to 50% of the previous rate. If fever recurs following infusion rate change, the investigator should assess the patient's level of discomfort with the event and use clinical judgment to determine if the patient should receive further ipilimumab.

#### **5.2.6.b Monitoring and Management of Immune-mediated Adverse Reactions**

Refer to Appendix B for algorithms recommended for utilization in CA184-187.

### **5.2.6.c Liver Function Test (LFT) Assessments Required Before Administration of Nivolumab or Ipilimumab**

Liver function tests (AST, ALT, T. bilirubin) will be evaluated for every subject prior to administration of nivolumab or ipilimumab. Blood samples must be collected and analyzed at local or central labs within 7 days prior to dosing. LFT results must be reviewed by the principal investigator (or designee) to meet dosing criteria specifications:  $\leq 2.5 \times \text{ULN}$  for AST, ALT and  $\leq 2 \times \text{ULN}$  for T. bilirubin unless liver metastases are present in which case LFT  $\leq 5 \times \text{ULN}$  for AST, ALT and T. bilirubin  $\leq 3.0 \times \text{ULN}$  prior to dosing.

If, during the course of treatment abnormal LFT values are detected, the subject must be managed using the hepatotoxicity algorithm section in Appendix B.

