## **1.5 Uveal Melanoma**

Uveal melanoma is the most common primary intraocular malignant tumor in adults and the second most common type of primary malignant melanoma in the body. It represents five to six percent of all melanoma diagnoses. The incidence of uveal melanoma in the world is approximately 4,800 persons per year with nearly 2,000 cases diagnosed in North America annually. Metastasis is via vascular spread, and approximately 40-50% of patients with uveal melanoma will ultimately develop distant disease. The liver is involved in up to 95% of individuals who develop metastatic disease. The clinical course of patients with uveal melanoma is determined by progression of the disease in the liver. Once metastatic disease is identified, the median survival of patients with liver metastases is six

to seven months, despite therapy, with a dismal one-year survival of approximately 10-15%.

Immunotherapy using checkpoint blockade inhibitors have made significant headway in cutaneous melanoma but their relevance in melanomas of rare subtypes, including uveal melanoma, remains unstudied in a prospective fashion. Anecdotal reports from expanded access programs and case reports of uveal melanoma patients treated with ipilimumab at both 3 mg/kg and 10 mg/kg demonstrate modest clinical activity at best with responses no more than 6%. CA184-187 was the first prospective ipilimumab trial in the world dedicated solely to uveal melanoma patients. After enrollment of 20 patients however, no documented responses were noted at both 3 mg/kg and 10 mg/kg.

Because of rationale behind combination checkpoint blockade inhibition and the notable clinical activity in cutaneous melanoma with a 1-year overall survival approaching that of targeted therapies (69% 1-year OS presented by Sznol et al. ASCO 2014), it is possible that monotherapy checkpoint blockade may not be enough to overcome tumor progression in uveal melanoma and that combination immunotherapy is in fact the necessary approach. Indeed, reports of small series of uveal melanoma patients on monotherapy anti-PD-1 clinical trials to date have failed to demonstrate any responses (nivolumab, MK-3475). Combination checkpoint blockade with nivolumab and ipilimumab at doses established in cutaneous melanoma warrant investigation in a prospective fashion for metastatic uveal melanoma patients.

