### 4.1 Inclusion Criteria

1. Willing and able to give written informed consent.
2. History of uveal melanoma and documented metastatic disease with at least one measurable lesion is required defined as  $\geq 1$  cm x 1 cm (on spiral CT or equivalent).
3. Any number of prior therapies is allowed.
4. Required values for initial laboratory tests:
  - WBC  $\geq 2000/uL$
  - ANC  $\geq 1500/uL$
  - Platelets  $\geq 100 \times 10^3/uL$
  - Hemoglobin  $\geq 9$  g/dL
  - Creatinine  $\leq 1.5$  x ULN or creatinine clearance (CrCl)  $\geq 40$  mL/min (using the Cockcroft-Gault formula):
    - Female CrCl =  $(140 - \text{age in years}) \times \text{weight in kg} \times 0.85$   
72 x serum creatinine in mg/dL
    - Male CrCl =  $(140 - \text{age in years}) \times \text{weight in kg} \times 1.00$
  - 72 x serum creatinine in mg/dL AST/ALT  $\leq 3$  x ULN for patients without liver metastasis,  
 $\leq 5$  x ULN for liver metastases
  - Bilirubin  $\leq 1.5$  x ULN, (except patients with Gilbert's Syndrome, who must have a total bilirubin less than 3.0 mg/dL)
5. In suspected patients, no active or chronic infection with HIV, Hepatitis B, or Hepatitis C.
6. Performance status ECOG 0-1.

7. Men and women,  $\geq 18$  years of age. Because no dosing or adverse event data are currently available on the use of ipilimumab in patients  $<18$  years of age, minors are excluded from this study.
8. Baseline imaging in the form of CT chest, abdomen, pelvis with oral and intravenous contrast within 28 days of study entry. For patients with a contrast allergy, choice of alternative body imaging will be at the discretion of the investigator or his designee. MRI of the brain is only needed if clinically indicated.
9. Prior to start of treatment must be more than 21 days elapsed from surgery, radiation therapy, or prior chemotherapy. More than 42 days elapsed from prior immune therapy including vaccines.
10. Women of childbearing potential (WOCBP) and fertile men with partners of childbearing potential must be using an adequate method of contraception to avoid pregnancy throughout the study and for up to 26 weeks after the last dose of investigational product, in such a manner that the risk of pregnancy is minimized.

WOCBP include any female who has experienced menarche and who has not undergone successful surgical sterilization (hysterectomy, bilateral tubal ligation, or bilateral oophorectomy) or is not post-menopausal. Post-menopause is defined as:

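### In limited ranges the pre-dose liver limits in 5.2.6.c disagree with the discontinuation rule in 5.2.3, the Appendix A hepatic footnote and the entry limits in 4.1, and no section says which prevails

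*Combined protocol and SAP*

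**What the plan says.** **Pre-dose check (5.2.6.c).** AST, ALT and total bilirubin "will be evaluated for every subject prior to administration of nivolumab or ipilimumab", and "LFT results must be reviewed by the principal investigator (or designee) to meet dosing criteria specifications". The limits are AST/ALT 2.5 × ULN and bilirubin 2 × ULN, "unless liver metastases are present in which case LFT" limits become 5 × ULN for AST/ALT and 3 × ULN for bilirubin. Abnormal on-treatment values are referred to a hepatotoxicity algorithm in Appendix B.

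**Discontinuation (5.2.3).** This mandatory list takes the subject off therapy and off study. On the liver it states: "Any drug-related liver function test (LFT) abnormality that meets the following criteria require discontinuation". The criteria are AST/ALT above 8 × ULN, bilirubin above 5 × ULN, or "Concurrent AST or ALT > 3 x ULN and total bilirubin > 2 x ULN". There is no separate limit for liver metastases.

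**Hepatic algorithm (Appendix A).** A footnote allows immunotherapy to be delayed instead of stopped while AST/ALT is at or below 8 × ULN and bilirubin at or below 5 × ULN.

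**Resumption (5.2.2, Criteria to Resume Treatment).** Combined AST/ALT and bilirubin elevation that meets the discontinuation parameters leads to permanent discontinuation. The parameters are said to be in Section 4.3.5.

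**Entry (4.1, item 4).** AST/ALT may be at most 3 "x ULN for patients without liver metastasis", or 5 × ULN with liver metastases. Bilirubin may be at most 1.5 × ULN, except in Gilbert's syndrome, for patients "who must have a total bilirubin less than 3.0 mg/dL".

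**Population (1.5).** "The liver is involved in up to 95% of individuals who develop metastatic disease".

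**The concern.** Someone deciding whether to give the next dose needs one answer for each set of liver results. For some results the protocol gives more than one.

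With liver metastases, a result can satisfy the explicit numeric pre-dose specification and also meet a criterion for mandatory discontinuation. The appendix that guides hepatic toxicity offers delay as a third course. The readings differ in drug exposure and in whether the subject stays on study. During induction both antibodies are affected; in maintenance, nivolumab alone. Section 6.2.1 puts hold-and-notify parameters on the infusion order set, so an order set built on 5.2.6.c alone would raise no hold for these values.

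Without liver metastases the mismatch runs the other way: a patient can meet the entry limit and fail the pre-dose limit on the same blood sample.

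**Working it through.** The plan states no figure on this point, so there is none to reproduce. The check treats each rule as a condition on A (the higher of AST and ALT) and B (total bilirubin), both in multiples of ULN, and looks for values where the rules give different actions.

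| Rule | Without liver metastases | With liver metastases |
|---|---|---|
| 4.1, eligible (non-Gilbert) | A ≤ 3 and B ≤ 1.5 | A ≤ 5 and B ≤ 1.5 |
| 5.2.6.c, meets dosing check | A ≤ 2.5 and B ≤ 2 | A ≤ 5 and B ≤ 3 |
| 5.2.3, discontinue if drug-related | A > 8, or B > 5, or (A > 3 and B > 2) | same |
| 5.2.4.a, liver limits for stopping ipilimumab | A > 5 or B > 3 | same |
| Appendix A footnote, delay possible | A ≤ 8 and B ≤ 5 | same |

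**1. Pre-dose check against discontinuation.**
- With liver metastases: {A ≤ 5, B ≤ 3} intersected with {A > 3, B > 2} gives 3 < A ≤ 5 together with 2 < B ≤ 3. The single-test criteria (A > 8, B > 5) lie outside the dosing limits, so only the concurrent criterion overlaps.
- Without liver metastases: A ≤ 2.5 excludes A > 3, so there is no overlap.
- Example with liver metastases, A = 4 and B = 2.5, judged drug-related: 5.2.6.c is met; 5.2.3 discontinues; the Appendix A footnote allows delay; the numeric liver limits of 5.2.4.a are not crossed.
- Timing: 5.2.3 needs a drug-related abnormality, so the conflict cannot occur before the first dose.

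**2. Entry against pre-dose check.**
- Without liver metastases: {A ≤ 3} minus {A ≤ 2.5} leaves 2.5 < A ≤ 3, eligible but not dosable until the value falls. Table 10 lets the baseline and Week 1 visits coincide, so one sample can serve both rules.
- With liver metastases: both AST/ALT limits are 5, so there is no gap. Non-Gilbert bilirubin has no gap in either group (1.5 against 2 or 3).

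**3. Gilbert's syndrome.** The entry limit of 3.0 mg/dL equals 3.0/ULN in multiples of ULN. It exceeds the 2 × limit when 3.0/ULN > 2, that is, when ULN < 1.5 mg/dL. The documents give no ULN. Assuming 1.0, 1.2 or 1.3 mg/dL, 3.0 mg/dL is 3.0, 2.5 or 2.3 × ULN. All three exceed 2, the limit without liver metastases; none exceeds 3, the limit with them.

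**4. Related disagreement.** For A above 5 and up to 8 with B ≤ 2, 5.2.4.a stops ipilimumab while the liver criteria of 5.2.3 are not met. These limits belong in the same reconciliation.

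**5. Cross-references.** Section 4 ends at 4.3, the data safety monitoring plan, so there is no Section 4.3.5. The algorithms are in Appendix A, and the table of contents lists no Appendix B.

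**6. Size.**
- Conflict 1 requires liver metastases, concurrent enzyme and bilirubin elevation in the stated ranges, and a drug-related judgement. For the combination, 1.3.6 gives treatment-related ALT and AST increases of 21% each, but no bilirubin rate. The frequency therefore cannot be calculated.
- Conflict 2 and the Gilbert gap concern patients without liver metastases. If 95% have liver involvement, 0.05 × 39 = 1.95, about 2 patients. Because 95% is given as an upper figure, the group could be larger. Only those with AST/ALT in a band 0.5 × ULN wide, or with Gilbert's syndrome and bilirubin above 2 × ULN, are affected.

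**The case against.** The strongest reply is that 5.2.6.c is a necessary check and not a sufficient one. It says what results must satisfy before dosing; it does not say that satisfying it cancels a stopping rule. Section 5.2.3 is mandatory and withdraws the subject, so no later pre-dose check would follow. The resumption criteria point the same way. Section 5.2.6.c itself sends abnormal on-treatment values to the hepatotoxicity algorithm, and a physician or designee reviews results before dosing.

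Much of this stands, and 5.2.3 is best read as controlling. A reader might infer that the protocol tells sites to dose patients who must stop; the text does not go that far. But the controlling reading has to be inferred. No section states precedence, the resumption criteria rely on a section that does not exist, and 5.2.6.c names an appendix that is not there. Following the algorithm in Appendix A instead leads to a footnote allowing delay for the same values. The chart which that footnote annotates could not be read here, so its exact scope should be confirmed.

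On entry, a stricter day-of-dose limit than the screening limit is not in itself an error. Nothing prevents a repeat sample, so it would be wrong to infer that such patients are never dosed or that they materially consume the 25% inevaluable allowance.

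**Conclusion.** The disagreement is real but confined to stated ranges.

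- With liver metastases, AST/ALT >3 to 5 × ULN together with bilirubin >2 to 3 × ULN meets the dosing check. If drug-related, it requires discontinuation under 5.2.3 and permits delay under Appendix A. It cannot arise at dose 1.
- Without liver metastases, AST/ALT >2.5 to 3 × ULN is eligible but not dosable until values fall.
- The missing Gilbert's counterpart matters without liver metastases if the ULN is below 1.5 mg/dL, which is an assumption.

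Three stronger readings are not supported. Liver-based dosing is not undefined in general: outside these ranges and the 5.2.4.a differences noted, the rules compared here do not collide. Neither 0.95 × 39 = 37 patients with liver metastases nor 0.21 × 39 = 8 with enzyme rises counts conflict cases, since concurrent bilirubin elevation and attribution are also needed; moreover, 39 includes screen failures. And the documents do not imply that every eligible patient must be dosable on day 1; that is a clinical rule for the sponsor.

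The point concerns safety and consistent conduct. It does not affect the response-rate decision rule for the 27 evaluable patients.

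**What to change.** Reconcile 4.1, the resumption criteria in 5.2.2, 5.2.3, 5.2.4.a, 5.2.6.c and the Appendix A hepatic footnote so that each liver result leads to one action. A single table by liver-metastasis status, Gilbert's status and drug-relatedness would do this. State which section takes precedence when more than one applies, in particular how 5.2.6.c stands to 5.2.3. Correct the references to Section 4.3.5 and Appendix B. Then align the infusion order-set hold parameters described in 6.2.1 with the reconciled text. All limits and clinical rules are for the sponsor to set.

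The cost is amendment wording with its usual approval and one order-set update. No new tests, visits or patients are needed.
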